8.2.4 Study discontinuation

Boehringer Ingelheim reserves the right to discontinue the study overall or at a particular study site at any time for the following reasons.

1. Failure to meet expected enrolment goals overall or at a particular study site

2. Emergence of any effectiveness/safety information that could significantly affect continuation of the study, or any other administrative reasons, i.e., lack of recruitment
3. Violation of Good Pharmacoepidemiology Practice (GPP), the study protocol, or the contract by a study site, investigator, or research collaborator, disturbing the appropriate conduct of the study

The investigator/the study site/research collaborator will be reimbursed for reasonable expenses incurred in case of study/site termination (except in case of the third reason).

Patients who discontinue from the study before the visit at week 52 will be asked to complete an EoT visit.

8.3 VARIABLES

The following parameters will be collected and assessed at visit 1 and/ or visit 2 and/or visit 3:

- Patient demographics (age, gender, height & weight)
- Concomitant diseases / comorbidities (relevant comorbidities such as cardiovascular diseases, diabetes mellitus type 2, depression and diseases affecting the preparing and handling of the Respimat® device)
- Date of confirmed COPD diagnosis [year]
- Start with inhalative bronchodilators for COPD treatment [year]
- Concomitant COPD medication including AICDs (dosage, date of onset) up to 6 weeks before baseline visit
- Changes in COPD treatment scheme (date, reason(s))
- Last available FEV1 (value and date measured) and FVC including % predicted (value and date measured, closest to the date of baseline visit)
- Reported moderate-to-severe exacerbations based on medical history in the last 12 months and exacerbations leading to hospitalization in the last 12 months
- Smoking history (number of pack years) and status (never, former, current)
- Assessment of the severity of breathlessness based on the mMRC questionnaire
- GOLD spirometric classifications (1, 2, 3, 4) and GOLD patient groups (A, B, C, D) based on GOLD-2022
- Clinical control based on CCQ score and CCQ symptom, mental state, and functional state domain scores

- (Safety Reporting*; Adverse Drug Reactions (serious and non-serious), fatal AEs, and pregnancies at the beginning and at the end of the study)

*Safety data will be collected descriptively and are not a separate objective of the NIS.

8.3.1 Exposures

All patients will switch from the Spiriva® HandiHaler® to Spiriva® Respimat® based on physician's decision which will be made prior to study inclusion basing on patient's individual medical needs and according to the current SmPC.

Spiriva® Respimat® contains

- the long-acting anticholinergic tiotropium bromide.

The dose dispensed is 2.5 micrograms of tiotropium per puff.

The recommended daily dose of Spiriva® Respimat® for adults is 5 micrograms of tiotropium, equivalent to inhaling 2 puffs from the Respimat® inhaler once daily at the same time of day.

The Summary of Product Characteristics (SmPC) [XX] on Spiriva® Respimat® is contained in the NIS investigator site file in the "Summary of Product Characteristics" section.

Note: The recommended doses stated in the SmPC should not be exceeded.

8.3.2 Outcomes

8.3.2.1 Primary outcomes

- Outcome type: primary
- Outcome name: "**Improvement**" defined as 0.2 points decrease in the CCQ score between baseline and visit 2 in patients with high CCQ baseline score (≥ 2)

- Time frame: between baseline (= visit 1) to approximately 8 weeks after switching from Spiriva® HandiHaler® to Spiriva® Respimat® (= visit 2)
- Safety Issue: No

8.3.2.2 Secondary outcomes

- Outcome type: secondary
- Outcome name: “**Improvement**” defined as 0.2 points decrease in the CCQ score between baseline and visit 2 in patients independently from CCQ baseline score
- Time frame: between baseline (= visit 1) to approximately 8 weeks after switching from Spiriva® HandiHaler® to Spiriva® Respimat® (= visit 2)
- Safety Issue: No
- Outcome type: secondary
- Outcome name: “**Changes in clinical control**” [[XXXIII](#)] defined as mean change in the in CCQ score and in the scores of the 3 CCQ subdomains symptom (items 1, 2, 5, 6 of the CCQ), mental state (items 3, 4 of the CCQ), and functional state domain (CCQ-4, items 7, 8, 9 and 10 of the CCQ), in all patients independently from CCQ baseline score
- Time frame:
 - between baseline (= visit 1) and approximately 8 weeks after switching from Spiriva® HandiHaler® to Spiriva® Respimat® (= visit 2)
- Safety Issue: No
- Outcome type: secondary
- Outcome name: “**Changes in clinical control**” defined as mean change in the in CCQ score and in the scores of the 3 CCQ subdomains symptom (items 1, 2, 5, 6 of the CCQ), mental state (items 3, 4 of the CCQ), and functional state domain (CCQ-4, items 7, 8, 9 and 10 of the CCQ), in patients with high CCQ baseline score (≥ 2)
- Time frame:
 - between baseline (= visit 1) and approximately 8 weeks after switching from Spiriva® HandiHaler® to Spiriva® Respimat® (= visit 2)
- Safety Issue: No

- Outcome type: secondary
- Outcome name: "**Breathlessness of the patients**" assessed by the mMRC scale completed by all patients
- Time frame: Assessment will be performed at baseline (= visit 1), approximately 8 weeks after switching from Spiriva® HandiHaler® to Spiriva® Respimat® (= visit 2)
- Safety Issue: No

- Outcome type: secondary
- Outcome name: "**Changes in breathlessness of the patients**" assessed by the mMRC scale completed by all patients
 - Time frame: between baseline (= visit 1) to approximately 8 weeks after switching from Spiriva® HandiHaler® to Spiriva® Respimat® (= visit 2)
- Safety Issue: No

8.3.3 Covariates

Not applicable.

8.4 DATA SOURCES

Medical records collected through routine clinical care will be used to assess the inclusion/exclusion criteria of patients. Such medical records will be used for patient

demographics, smoking history, collection of previous COPD medication, concomitant diseases, and previous exacerbation history.

All patients will be enrolled consecutively. The study physician has the ultimate responsibility for the collection and reporting of all clinical and patient data through the case report forms (CRFs) as well as ensuring that they are accurate and complete.

Start of treatment will be assessed by a yes/no question at visit 2. If treatment was started, date of treatment onset will be asked by the physician.

The CCQ comprises 10 items. Each question can be scored by patients on a 7-point scale between 0 and 6. The sum of the scores divided by 10 gives the CCQ score. For the functional status calculation, the sum of the 4 items (# 7, 8, 9, 10) is divided by 4, for the symptom domain the sum of the 4 items (# 1, 2, 5, 6) is divided by 4, and for the mental state domain the sum of the 2 items (# 3, 4) is divided by 2. This questionnaire will be filled out by the patient and entered in the database by trained personnel from the Clinical Research Organization. Patients will be asked to complete the CCQ to evaluate their clinical control before, approximately 8 weeks after treatment with Spiriva® Respimat®.

The modified Medical Research Council (mMRC) scale will be used to assess the breathlessness state of the patient before switching the device, and approximately 8 weeks after device switch. The mMRC stage (0 to 4) collected from the patient as well as the exacerbation history will be used to calculate the GOLD patient group (B, C, or D) in the CRF.

8.5 STUDY SIZE

It is expected that half of the patients included will have CCQ score of ≥ 2 (high CCQ).

Primary endpoint: Assuming 40% of high CCQ score patients have a 0.2 improvement in CCQ score from baseline at 8 weeks on treatment, then with a sample size of 100, the 95% CI for the response rate will be: (0.304, 0.496).

Secondary endpoint: Assuming 30% of all patients have a 0.2 improvement in CCQ score from baseline at 8 weeks on treatment, then with a total sample size of 200, the 95% CI for the response rate will be (0.236, 0.364).

With a dropout rate of 10%, a total of about 225 patients will be needed.

Sample size assumes that Respimat® is better compared to HandiHaler® and patients will improve their CCQ scores once switched to Respimat®. The sample size calculation/justification can only provide a rough estimate of the statistical power in such an exploratory real-world setting. Recruitment will continue until the minimum sample size is achieved.

8.6 DATA MANAGEMENT

The data management plan is summarized below. Full details of the data management plan are documented in a separate NIS-Data Management and Review Plan (NIS-DMRP).

A data management plan (DMP) will be created to describe all functions, processes, and specifications for data collection, cleaning, and validation. Boehringer-Ingelheim will check CRFs for correctness at date of collection. The CRFs will be sent to the vendor or Clinical Research Organization (CRO) and will be computed by trained staff from the vendor/CRO including programmable edits to obtain immediate feedback if data are missing (also negative answers, unknown), out of range, illogical or potentially erroneous. These rules may encompass simple checks such as range validation or presence/absence of data.

Concurrent manual data review may be performed based on parameters dictated by the DMP. Ad hoc queries to the sites may be generated and followed up for resolution. A source data quality audit may be initiated to ensure that the data in the database is accurate. Source data verification (SDV) will be performed at sites identified by a risk-based approach as needed.

The database will be housed in a physically and logically secure computer system maintained in accordance with a written security policy. The system will meet the standards of the International Committee on Harmonization guideline E6R1 regarding electronic study data handling and the safety requirements of the FDA (US Food & Drug Administration) concerning systems for the data acquisition of clinical studies in accordance with "Title 21 Code of Federal Regulations (21 CFR Part 11): Electronic Records; Electronic Signatures". Patient confidentiality will be strictly maintained.

8.7 DATA ANALYSIS

This section provides specifications for the preparation of the final statistical analysis plan (SAP), which will be issued prior to database lock. Any differences compared to this statistical section should be identified and documented in the final SAP.

The following data handling conventions will be followed:

- Baseline assessments are those that were completed at the baseline visit (visit 1).
- The following analysis time windows will be utilized in the analysis:
 - Assessments scheduled to be done:
 - Approximately 8 weeks after treatment start (= visit 2): 8 weeks \pm 2 weeks
 - Approximately 52 weeks after treatment start (= visit 3, follow-up visit): 52 weeks \pm 4 weeks
 - If patients discontinue or switched from Spiriva® Respimat® treatment, they will be asked to perform an EoT visit (= visit 3) nearby to the date of stopping Spiriva® Respimat® treatment

No formal hypothesis testing will be performed since this is a self-controlled study. The analysis of the data will be of descriptive and explorative character. Variables will be summarized using appropriate statistical methods

The statistical characteristics presented in the end-of-text tables will be N / mean / SD / min / median / max for continuous variables. Tabulations of relative and absolute frequencies will be presented for categorical variables. Proportions and 95% CI will be given when appropriate.

At baseline, the following data will be collected as available in routine clinical practice:

Patient demographics and medical history:

- Patient demographics (gender, age, height, weight)
- Comorbidities (main diagnosis and concurrent diagnosis according to MedDRA, version valid at the time of database closure)
- COPD related concomitant medication (according to the WHO classification, version valid at the time of database closure)
- Details of treatment with inhaled respiratory agents before the study
- History of smoking
- GOLD spirometric classifications (1, 2, 3, 4) and GOLD patient groups (A, B, C, D), date of confirmed COPD diagnosis

Data collection at baseline:

- Breathlessness based on mMRC score at visit 1; secondary endpoint

- CCQ score and CCQ symptom, mental state, and functional state scores; secondary endpoint

■ [REDACTED]

■ [REDACTED]

■ [REDACTED]

The following data will be collected as available in routine clinical practice at visit 2:

- Assessment of treatment start with date of onset, if applicable
- Breathlessness based on mMRC score, secondary endpoint
- CCQ score and CCQ symptom, mental state, and functional state scores; secondary endpoint

■ [REDACTED]

- Reasons for ending treatment during the observational period

- Details of treatment continuation / discontinuation

- Adverse Drug Reactions (ADR & SADR), fatal AEs, pregnancies (descriptive collection, no endpoint of the current study).

The following data will be collected as available in routine clinical practice at visit 3 (follow-up visit)/EoT vis:

- Details of treatment with respiratory agents during the study and changes (if applicable)
- Reasons for ending treatment during the observational period
- Details of treatment continuation / discontinuation

- Adverse Drug Reactions (ADR & SADR), fatal AEs, pregnancies (descriptive collection, no endpoint of the current study).

All statistical analyses will be pre-specified in the SAP. Statistical analysis will be performed by using SAS Version 9.4 or higher.

8.7.1 Main analysis

For the primary outcome, the proportion of patients (%) with a CCQ decrease of at least 0.2 points and a high CCQ baseline score of ≥ 2 will be presented together with the 95% confidence interval.

8.7.3 Safety Analysis

All adverse events and adverse drug reactions collected per study protocol will be included and summarized in the in the final study report according to local requirements.

8.8 QUALITY CONTROL

All details are documented in the NIS-DMRP.

Every physician shall allow an authorized personal or staff from Boehringer Ingelheim (Schweiz) GmbH to make regular visits to monitor the study. The monitor will either use interviewing techniques for monitoring or perform source data verification. The CRF entries will be compared with the data given in the patient files. Therefore, in order to perform an extend source data verification the monitor shall have access to the patient files. Furthermore, the CRFs will be controlled for completeness and accuracy.

Visiting of the study and laboratory facilities will likewise be allowed.

During data entry, incomplete or non-valid data will be identified, and data clarification requests will be sent to the physician.

Completed CRFs should be returned at the end of each month to the responsible study manager to accelerate the process of data entry and evaluation. In case of return after more than 3 months after completion acceptance of the CRF cannot be ensured. The physician/investigator or a qualified designee will be responsible for recording and verifying the accuracy and correctness of patient data within the CRF via signature.

Data will be entered and verified for accuracy by trained personal from Boehringer Ingelheim (Schweiz) GmbH / CRO /vendor according to the data entry manual. A sample of 10% of all CRFs will be double-checked by an independent person. Data will be checked during patient enrolment for consistency, plausibility, and out-of-range values by responsible Data Management staff. These checks will be performed through programs and range checks within the EDC system.

8.9 LIMITATIONS OF THE RESEARCH METHODS

The intention of this NIS is to collect data on the changes in HRQoL in patients with COPD after switching from Spiriva® HandiHaler® to Spiriva® Respimat® in a real-world setting.

A NIS appears the most suitable instrument for obtaining information about the use of medicines in everyday therapeutic practice and thus for investigating future questions in everyday therapeutic practice.

Consecutive enrolment will be employed to minimize selection bias. The entry criteria are non-restrictive which will permit the enrolment of a broad patient population. The choice of treatment is at the discretion of the investigator.

Selection bias could occur at the site level and the patient level. To minimize the site level selection bias, the goal is to have participating centers that have access to all available treatment options which are approved for use in Switzerland for the targeted COPD patients. To minimize selection bias at the patient level, consecutive enrolment is performed. Information bias will be minimized using standard CRF, questionnaire and physicians' training on the study protocol.

8.10 OTHER ASPECTS

8.10.1 Data quality assurance

A quality assurance audit/inspection of this study may be conducted by the sponsor or sponsor's designees or by Institutional Review Board (IRBs) / Independent Ethics Committee (IECs) or by regulatory authorities. The quality assurance auditor will have access to all medical records, the investigator's study-related files and correspondence, and the informed consent documentation of this study.

8.10.2 Study records

Case Report Forms (CRFs) for individual patients will be provided by the sponsor, in paper or electronic Form.

8.10.2.1 Source documents

Source documents provide evidence for the existence of the patient and substantiate the integrity of the data collected. Source documents are filed at the investigator's site.

Data reported on the CRFs that are transcribed from source documents must be consistent with the source documents or the discrepancies must be explained. The investigator may need to request previous medical records or transfer records, depending on the study; also current medical records must be available.

For CRFs, the following data need to be derived from source documents:

- Patient identification (gender, date of birth)
- Patient participation in the study (substance, study number, patient number, date patient was informed)

- Dates of patient's visits, including prescription of study medication
- Medical history (including study indication and concomitant diseases, if applicable)
- COPD medication history
- Adverse events and outcome events (onset date (mandatory), and end date (if available))
- Serious adverse events (SAEs) (onset date (mandatory), and end date (if available))
- Originals or copies of laboratory results (in validated electronic format, if available)
- Conclusion of patient's participation in the study
- Questionnaires and surveys completed by the patient

■ [REDACTED]

8.10.2.2 Direct access to source data and documents

The investigator/institution will permit study-related monitoring, audits, IRB/IEC review and regulatory inspection, providing direct access to all related source data/documents. CRFs and all source documents, including progress notes and copies of laboratory and medical test results must be available at all times for review by the sponsor's clinical study monitor, auditor and inspection by health authorities (e.g., Swissmedic). BI study staff and auditor may review all CRFs and written informed consents. The accuracy of the data will be verified by reviewing the documents described in Section [8.10.2.1](#).

8.10.3 Completion of study

The IEC/competent authority in Switzerland needs to be notified about the end of the study (last patient/patient out, unless specified differently in Section [9.1](#)) or early termination of the study.

8.10.4 Protocol deviations

Protocol deviations will be specified in the SAP. Patients with protocol deviations will be excluded from the full analysis set.

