6.3 ASSESSMENT OF QUALITY OF LIFE

Various questionnaires on HRQoL are used to try assessing COPD patients' health status and physical state. The Clinical COPD questionnaire (CCQ) has been developed and validated in the Netherlands especially for COPD patients by Jan Kocks et al. in 2006 [XXIX] to categorize

patients' impairments generally and focus patients' treatment on their specific needs. The CCQ is easy to administer, and it takes less than a few minutes to complete. CCQ is used to monitor the clinical control of COPD covering the last 7 days prior to request. It consists of 10 questions, covering 3 domains: symptom domain (4 items [#'s 1,2,5,6]); functional status domain (4 items [#'s 7,8,9,10]) and mental status domain (2 items [#'s 3,4]). The questionnaire is responsive to intervention and has been translated and validated in over 140 languages [XXX]. In a head-to-head comparison of COPD Assessment Test (CAT) and CCQ the patients preferred the latter as it reflected their status better than CAT by giving more details on breathing problems which was more important for them than sleep or energy [XXX]. CCQ has been given maximum ranking in "COPD wellness tools" overview by the International Primary Care Respiratory Group (IPCRG) [XXXI]. The clinical CCQ is a well-established tool to evaluate COPD patients self-reported outcomes [XXIX, XXXII, XXXIII]. A difference from -0.2 points corresponds to 50% of the minimal clinically important difference for a CCQ of -0.4 points [XXIX, XXXII]. Patients with a worse CCQ (score of ≥ 2) are expected to have a CCQ score that is on average 0.2 points higher (i.e., worse health status) than patients with an acceptable CCQ score for moderate disease (score of < 2) [XXXIV]. Thus, a change of -0.2 points will be used in this NIS to explore whether there is an improvement in CCQ after switching the device without changing the pharmacological compound although the setting in this NIS is different from the validation studies.

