8. RESEARCH METHODS

8.1 STUDY DESIGN

This is a national, multicenter, non-interventional, observational, cohort study based on newly collected data with an observational period of at least 8 weeks until switch or discontinuation of Spiriva® Respimat® treatment or up to 52 weeks after baseline visit whatever occurs first.

This NIS is designed as single-arm study without a specific comparator in a parallel arm. All included patients must have been on treatment with Spiriva® HandiHaler® for at least 6 weeks prior to study inclusion. Therefore, patient could serve as their own control (baseline values) and a parallel arm being on Spiriva® HandiHaler® is not obligatory to address the primary objective of the NIS.

The study is non-interventional on the therapeutic strategy as the decision to switch the patient from Spiriva® HandiHaler® to Spiriva® Respimat® device is made by the treating physician prior to study inclusion due to patient's individual needs. Patients will be treated within clinical routine practice and according to the current standard of care to assess the real-world situation in Swiss clinical practice. The patients included in the study will be followed for 1 year (approximately 52 weeks) after switching to the Respimat® device with no fixed study visit schedule. The treating physician will be asked to record data for study endpoint assessments in week 8 after baseline to assess therapeutic success of the switch to the Respimat® device. Patients who discontinued Spiriva® Respimat® treatment or who were switched to another treatment will be asked to perform an end-of-treatment (EoT) visit (= follow-up visit).

This national study will be conducted as a multicenter study to collect information on current status, and characteristics of patients switching from HandiHaler® to Respimat® device from

various sites to achieve balanced data with regard to geographic distribution, type of clinical setting (e.g., academic versus community health centers), and prescriber specialty which are representative for the larger patient and prescriber community.

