8.2.2 Study population

Patients will be enrolled consecutively in the study. The decision to switch the patient from Spiriva® HandiHaler® to Spiriva® Respimat® will be made by the treating physician to the patient's need and to the standard of best medical practice prior to the inclusion into the study.

Patients with COPD planned to be switched according to the respective SmPC and consenting to participate in the study are eligible. To avoid any selection bias, all eligible patients will be invited to participate in this study, in the order in which their eligibility is determined. A time window of 1 years is foreseen for recruitment of the patients. Patients will be treated within clinical routine practice and according to the current standard of care. Patients who discontinue from treatment before the visit at week 52 will be asked to complete an EoT visit.

Inclusion criteria:

Patients can be included if all following criteria are met:

- Participants ≥ 40 years of age at baseline visit
- Patients with confirmed diagnosis of COPD*
- Patients who have been on Spiriva® HandiHaler® for ≥ 6 weeks at baseline visit
- Patients for whom a switch from Spiriva® HandiHaler® to Spiriva® Respimat® was planned prior to study inclusion. If additional inhalative COPD drugs (AICDs) are

used: AICD treatment must have been stable for at least 6 weeks before study inclusion

- Signed written informed consent form to participation

*Confirmed by spirometry: FEV1/FVC <0.7 (last available FEV1 and FVC including % predicted)

Exclusion criteria:

- Patients who have contraindications to Spiriva® Respimat® according to the current prescribing information label/ summary of product characteristics (SmPC)
- Patients who have signs of a current, acute respiratory tract infection 2 weeks prior visit 1
- Patients for whom further follow-up will not be possible at the enrolling site during the planned observational period (of approximately 8 weeks)
- Patients with confirmed diagnosis of only asthma
- Patients who had > 1 moderate to severe exacerbation(s) within the last 6 weeks prior to study inclusion
- Patients who are pregnant or breastfeeding
- Patients participating in an ongoing interventional study

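### Section 8.10.4 removes patients with protocol deviations from the full analysis set without limiting this to consent or baseline eligibility failures, so the set behind the primary proportion may be a per-protocol set

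*Combined protocol and SAP*

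**What the plan says.** Section 8.10.4 has two sentences. The first defers the definition: "Protocol deviations will be specified in the SAP". The second fixes the consequence: "Patients with protocol deviations will be excluded from the full analysis set". There is no qualifier such as major, important or eligibility-related, and no restriction to events before the switch.

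Section 8.7.1 gives the primary result as "the proportion of patients (%) with a CCQ decrease of at least 0.2 points and a high CCQ baseline score" of 2 or more, with a 95% confidence interval. It names no analysis set. The full analysis set is mentioned only in section 8.10.4, and no per-protocol or other set is named in the visible text. Section 8.7.2 is not visible, parts of the protocol are redacted, and the SAP's deviation list is not in the supplied text. Nothing is assumed here about what those parts contain.

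**The concern.** A full analysis set normally keeps eligible patients in, whatever happens to them later. Here the only visible rule about the set takes patients out, and it treats a patient who should never have been enrolled in the same way as one whose deviation arose after the switch.

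The distinction matters because the primary result is a single-arm proportion. There is no comparator in which similar exclusions might partly cancel, so anyone removed from the denominator changes the estimate directly. If removal depends on post-switch events related to outcome, the reported rate describes a selected group. That would also work against the protocol's own aim: sections 8.2.2 and 8.9 rely on consecutive enrolment to limit selection bias, and an unrestricted exclusion could bring selection back at the analysis stage.

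The study is descriptive, with no formal hypothesis test (section 8.7). What is at stake is a biased and slightly less precise estimate, not a type I error rate.

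**Working it through.** **Inputs from the protocol (section 8.5).** Expected improvement rate among high-CCQ patients: 0.40. Planned number for the primary endpoint: 100. Total enrolment: about 225. Dropout: 10%. Share with high CCQ: one half.

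**Assumptions, not in the documents.** Share of high-CCQ patients excluded for deviations, f: 5% or 10%. Improvement rate among those excluded, p: 0% to 60%.

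**1. The plan's own interval.** Half-width = 1.96 × √(0.40 × 0.60 / 100) = 0.096. The interval is 0.40 ± 0.096 = 0.304 to 0.496, which matches section 8.5.

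**2. Patients affected.** High-CCQ patients expected with data: 225 × 0.9 × 0.5 = 101.25. Excluded at 5%: about 5. Excluded at 10%: about 10.

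**3. Bias of the reported rate.** Let retained patients improve at 0.40, which is then the reported rate. The rate in all eligible patients is (1 − f) × 0.40 + f × p. Reported minus actual is therefore f × (0.40 − p).

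| Excluded (f) | p = 0% | p = 20% | p = 40% | p = 60% |
|---|---|---|---|---|
| 5% | +2.0 points | +1.0 | 0 | −1.0 |
| 10% | +4.0 points | +2.0 | 0 | −2.0 |

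**4. Sensitivity to the anchor.** If 0.40 is instead the rate in all patients, the reported rate after exclusion is (0.40 − f × p) / (1 − f). With f = 10% and p = 20% this is (0.40 − 0.02) / 0.90 = 0.422, or +2.2 points in place of +2.0. With p = 0% it is 0.40 / 0.90 = 0.444, or +4.4 in place of +4.0. The choice of anchor makes little difference.

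**5. Precision.** Section 8.5 allows for dropout only. Excluding a further 5% or 10% leaves 101.25 × 0.95 ≈ 96 or 101.25 × 0.90 ≈ 91 patients, below the planned 100. At a rate of 0.40 with 91 patients the half-width is 1.96 × √(0.24 / 91) ≈ 0.101, against 0.096 planned. The loss of precision is small.

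**The case against.** The strongest reply is that the protocol sends the deviation list to the SAP. In a non-interventional study, where treatment and visits follow routine care, that list may consist mainly of consent and eligibility failures. If so, there is no post-switch selection. Section 8.7.2 is also not visible, so the absence of another set may partly reflect missing text. Both points stand and limit the finding. They do not remove it: only the list is deferred, the consequence is already fixed in section 8.10.4, and nothing visible requires the list to be narrow.

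It is also fair that the size rests on assumed rates and is modest. Much larger shifts can be produced by assuming that 20% to 30% of patients deviate and that few of them improve, but nothing in the documents supports such figures. Nor do the documents support the inference that exclusion would inflate the result; the direction is unknown.

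Two stronger readings are tempting and should be set aside.

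- **Visit window.** A reader might infer that a visit 2 outside 8 ± 2 weeks is a deviation that removes the patient, given that follow-up runs "with no fixed study visit schedule". But section 8.7 lists the window among its data handling conventions, under the words "The following analysis time windows will be utilized in the analysis". The natural reading is an analysis convention, not a conduct rule.
- **Timing.** A reader might infer that the deviation list could be settled after topline results are known, because the SAP is due before database lock and topline follows visit 2 of the last patient enrolled. But section 8.7 also says that all statistical analyses will be pre-specified in the SAP. Topline is such an analysis, so on a plain reading the SAP comes first.

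**Conclusion.** The point holds as a defect in a stated rule. As written, section 8.10.4 permits post-baseline deviations to remove patients from the only analysis set named in the visible text. Whether this causes bias depends on the SAP list: none of this kind if it is confined to consent and baseline eligibility failures, and otherwise a possible bias in either direction. Under the assumptions above the shift runs from about +4 to −2 points, less than half of the planned 9.6-point half-width even at its largest. That is modest, but the correction is cheap and worth making. No defect is claimed in the visit window, the SAP timing or the sample-size figures.

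**What to change.** Replace the second sentence of section 8.10.4 with:

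> The full analysis set includes all consented patients who met the inclusion and exclusion criteria at baseline and have a baseline CCQ, except patients documented as never having started Spiriva Respimat, regardless of deviations arising after baseline. Patients with important post-baseline deviations, as listed in the SAP, are excluded only from a separately named per-protocol set used for a sensitivity analysis. Numbers and reasons for exclusions are reported.

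In section 8.7.1, name the full analysis set, restricted to baseline CCQ ≥ 2, as the set for the primary proportion.

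Two details of the wording are deliberate. Breaches of baseline criteria stay out because they can distort the baseline itself. One exclusion criterion is "Patients who have signs of a current, acute respiratory tract infection 2 weeks prior visit 1", and "CCQ is used to monitor the clinical control of COPD covering the last 7 days prior to request"; a temporarily raised baseline could then fall for reasons unrelated to the device. Treatment start is phrased as a documented non-start because section 8.4 and Table 8.2.3:1 record it only at visit 2. Requiring a confirmed start would leave membership undeterminable for patients who miss that visit, and would bring back selection on a post-baseline event. How a missing visit 2 CCQ is handled remains a matter for the SAP, as section 7 already provides, and is separate from this point.

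Optionally, add one sentence to section 8.7 confirming that the 8 ± 2 week window is a data-handling convention and not a protocol deviation.

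The cost is protocol and SAP wording, one extra sensitivity row and a count of exclusions with reasons. No new data are needed. The primary rate may change slightly, in either direction.
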